1. INTRODUCTION

This Statistical Analysis Plan (SAP) is based on the final Clinical Study Protocol DSXS1538b (Study No. 71615001) Rev. 1 dated 06/28/2016. The SAP provides details on the planned statistical methodology for the analysis of the study data. The SAP also outlines the statistical programming specifications for the tables, listings and figures.

This SAP describes the study endpoints, derived variables, anticipated data transformations and manipulations, and other details of the analyses not provided in the study protocol. This SAP therefore outlines in detail all other aspects pertaining to the planned analyses and presentations for this study.

The following documents were reviewed in preparation of this SAP:

- Clinical Study Protocol DSXS1538b (Study No. 71615001) Rev. 1 dated 06/28/2016
- Case Report Form Booklet Version 1.0 for Study No. 71615001 (DSXS1538b)

The reader of this SAP is encouraged to also read the clinical protocol for details on the conduct of this study, and the operational aspects of clinical assessments and timing for completing a patient in this study.

2. OBJECTIVES

The objectives of this study are to:

1. Evaluate the potential of desoximetasone 0.25% shampoo to suppress HPA axis function in patients with moderate to severe scalp psoriasis.
2. Evaluate the efficacy parameters and adverse event (AE) profiles of desoximetasone 0.25% shampoo administered to patients with moderate to severe scalp psoriasis.

3. OVERALL STUDY DESIGN

This open-label, safety study is designed to evaluate the potential for adrenal suppression after maximal use treatment with desoximetasone 0.25% shampoo (Taro Pharmaceuticals, U.S.A.), for the treatment of moderate to severe scalp psoriasis.

Up to 5-10 eligible patients with stable plaque psoriasis of the scalp that satisfy all eligibility criteria will be enrolled into the study at Visit 1. Patients must be overall in good health. They should have a current diagnosis of moderate to severe scalp psoriasis with IGA score of at least 3 or 4.

**NOVUM PHARMACEUTICAL RESEARCH SERVICES
STATISTICAL ANALYSIS PLAN**

IND # 124879

Protocol/Study No. DSXS1538b/71615001

Desoximetasone 0.25% Shampoo

Patients enrolled in the study will apply product once daily for 28 days, according to provided instructions. Each patient is expected to receive 28 doses of study product.

Patients will attend a total of 3 Clinic Visits and a telephone follow-up phone call (Visit 4) as follows:

- **Visit 1 (Day 1):** Enrollment
- **Visit 2 (Day 14±2):** Interim Visit
- **Visit 3 (Day 29 ± 2):** End of Study or Early Termination
- **Visit 4 (Day 42± 4):** Follow-up Telephone Phone Call

The primary endpoint is the proportion of patients in the study with HPA axis suppression following treatment with the study medication.

The safety profile of each treatment group will be evaluated by comparing adverse events.

NOVUM PHARMACEUTICAL RESEARCH SERVICES
STATISTICAL ANALYSIS PLAN

IND # 124879

Protocol/Study No. DSXS1538b/71615001

Desoximetasone 0.25% Shampoo

Study Schematic

	Visit 1	Visit 2	Visit 3	Visit 4
Day	1	14 ± 2	29 ± 2	42 ± 4
Procedures	Screening/ Enrollment Before 12 pm	Interim Visit	End of Study/Early Termination Before 12 pm	Telephone Follow-Up Visit
Informed Consent	X			
Medical History and Demographics	X			
Vital Signs	X	X	X	
Pregnancy Test*	X	X	X	
Physical Exam	X		X	
HEENT Exam	X	X	X	
% Scalp Affected	X	X	X	
Investigator Global Assessment	X	X	X	
Concomitant Medication	X	X	X	X
Laboratory Evaluations	X		X	
Cortisol Response Test	X		X	
Confirm Inc/Exc Criteria	X			
Dispense Wristband	X			
Weigh and Dispense Study Product	X	X		
Collect and Weigh Study Product		X	X	
Dispense/Review Patient Diary	X	X	X	
Ocular Assessment		X	X	
Adverse Events		X	X	X
Evaluation of Patient Compliance to the Protocol		X	X	

* Pregnancy test will be carried out for females of childbearing potential.

**NOVUM PHARMACEUTICAL RESEARCH SERVICES
STATISTICAL ANALYSIS PLAN**

IND # 124879

Protocol/Study No. DSXS1538b/71615001

Desoximetasone 0.25% Shampoo

4. SAMPLE SIZE

The sample size of 5-10 evaluable patients was deemed appropriate to meet the objective of the study.

5. STUDY ENDPOINTS AND ANALYSIS POPULATIONS

Primary Outcome Measures:

Hypothalamic Pituitary Adrenal (HPA) Axis Response to Cosyntropin demonstrating the absence or presence of adrenal suppression at the end of treatment defined by the following criteria: 30 minute post Cortrosyn™ injection level cortisol level of \leq 18 mcg/100ml during the Cortisol Response Test.

The primary endpoint is the proportion of patients in the study with HPA axis suppression following treatment with the study medication.

Safety Population:

Safety Population includes all patients who applied at least one dose of study drug.

6. STATISTICAL ANALYSIS METHODS

If not otherwise specified, statistical significance is defined as $p<0.05$ and is two-tailed. Data will be summarized with respect to demographic and baseline characteristics, efficacy variables and safety variables.

For categorical variables, the number and percent of each category within a parameter will be calculated for non-missing data. For continuous variables, statistics will include number of observations, mean, standard deviation, median, minimum and maximum values.

All statistical analyses will be conducted using SAS®, Version 9.4 or higher. Datasets will be prepared using headings from Clinical Data Interchange Consortium (CDISC) Study Data Tabulation Model (SDTM) implementation for human clinical trials and ADaM (Analysis Dataset Model).

6.1 Baseline Characteristics

6.1.1 Demographics

Demographic information collected at baseline includes the following:

- Age (years)
- Gender (Male/Female)

**NOVUM PHARMACEUTICAL RESEARCH SERVICES
STATISTICAL ANALYSIS PLAN**

IND # 124879

Protocol/Study No. DSXS1538b/71615001

Desoximetasone 0.25% Shampoo

- Ethnicity (Hispanic/non Hispanic)
- Race (White, Black/African American, Native Hawaiian or Other Pacific Islander, Asian, American Indian or Alaska Native, Other)

Summary tables will be presented. Continuous variables will be summarized using descriptive statistics (n, median, minimum, maximum, mean, standard deviation). Categorical variables will be summarized using frequencies and percentages.

All data will be listed by patient.

6.1.2 Medical History

At Visit 1, patients will be questioned about medical history, including acute and chronic medical history and medical history relevant to their scalp psoriasis.

Medical history data will be listed by patient.

6.1.3 Physical Exam

A general physical exam will be conducted at Visit 1 and Visit 3. The physical exam must include a dermatological examination as a minimum.

Abnormal physical exam results will be listed by patient and visit.

6.1.4 Percent Scalp Affected

Patient's scalp will be examined by Investigator/designated clinician to determine the percent surface area affected with plaque psoriasis at all visits.

Descriptive summary (n, mean, standard deviation, median, minimum, maximum) will be presented for percent scalp affected by visit.

Percent scalp affected will be listed by patient and visit.

6.1.5 Pregnancy Test

Urine pregnancy tests on females of child-bearing potential will be performed at Visit 1, 2 and 3.

Positive pregnancy test results will be listed by patient and visit.

NOVUM PHARMACEUTICAL RESEARCH SERVICES
STATISTICAL ANALYSIS PLAN

IND # 124879

Protocol/Study No. DSXS1538b/71615001

Desoximetasone 0.25% Shampoo

6.1.6 Concomitant Medications

At Visits 1-3 and during the telephone follow-up phone call (Visit 4) patients will be questioned about current and concomitant medication use over the previous 12 weeks. At all Interim Visits patients will be questioned about ongoing or new concomitant medication use.

All prior and concomitant medications taken since screening will be listed by patient.

6.2 Statistical Analyses

6.2.1 Safety Analysis of Potential HPA Axis Suppression

Dosing will be once daily for 28 days. Patients who have normal adrenal function at baseline, use at least 21 doses of the study product and have data from a post-treatment cortisol response test will be included in the analysis.

The primary analysis of interest is to assess the proportion of patients considered to have demonstrated possible HPA axis suppression following treatment with the study medication.

A logistic regression of the proportion of patients in the study with HPA axis suppression may be performed as exploratory analysis with % scalp affected as a covariate. This will depend on the distribution of the % scalp data collected. See Appendix D for results from the cortisol response test considered indicative of potential HPA axis suppression.

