7.3 Scientific and Statistical Considerations

In some instances high potency steroids applied topically have been known to cause suppression of the hypothalamic-pituitary-adrenal (HPA) axis. In order to assess HPA axis function plasma levels of cortisol are measured before (basal) and after a bolus administration of synthetic α 1-24-adrenocorticotropic hormone (ACTH). In this study Cortrosyn™ (cosyntropin, a synthetic subunit of ACTH) (Amphstar Pharmaceuticals, Inc.) will be used according to manufacturer instructions to assess HPA axis function (See Appendices D, E).⁹ Recovery from steroid-induced adrenal insufficiency is usually rapid after the treatment is withdrawn.¹⁰ See Appendix D for further explanation of the evaluation of the role of topical corticosteroids in HPA axis suppression.

Taro Pharmaceuticals U.S.A. has recently completed an open label safety and efficacy study to assess adrenal suppression in adults with moderate to severe plaque psoriasis after 4 weeks of treatment under maximal use conditions with the test product, desoximetasone 0.25% spray. Of 21 evaluable subjects, adrenal suppression was identified in 1 of 12 subjects having involvement of 10-15% of body surface area (BSA) and 2 of 9 subjects having involvement of > 15% of BSA after treatment with Topicort® Topical Spray twice a day for 28 days. Adrenal function returned to normal at the first follow-up visit, which was 28 days after the end of treatment, for all 3 of these patients¹¹

This study design is based on similar studies performed, submitted and accepted by the FDA for recently approved high potency spray and foam topical corticosteroid formulations, topical corticosteroid/topical vitamin D3 analogue combination agents, and recommendations from the FDA in IND 101789 Guidance Meeting that took place on 01/14/2015 and an FDA Advice Letter dated 04/27/2015 (Reference ID: 3740601) for desoximetasone 0.15% topical spray, and recommendations provided by the FDA in the Meeting Request – Written Reponses Letter dated 09/18/2013 for PIND 118881 (Reference ID 3374240) for desoximetasone 0.25% shampoo.^{9,12-15}

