9.3.4 Removal of Patients from the Study

Patients will be advised that they are free to withdraw from the study at any time for any reason or, if necessary, the Investigator may withdraw a patient from the study to protect the health of that patient. A patient may also be withdrawn for not complying with study procedures. The clinical report will include all reasons for early withdrawals.

CONFIDENTIAL PROTOCOL

An Open Label, Safety Study to Assess the Potential for Adrenal Suppression Following Maximal Use Treatment with Desoximetasone 0.25% shampoo(Taro Pharmaceuticals U.S.A., Inc.) in Patients with Scalp Psoriasis

All patients who administer at least one dose of randomized study medication will be included in the safety analysis. If a patient terminates from the study early, all efforts will be made to complete their next visit study procedures. In case of early termination the Investigator shall fully document the reason for early termination. Reasons for early termination may include the following:

- Patient withdrew consent
- Significant adverse event that led the Investigator or patient to withdraw for safety reasons
- Worsening signs/symptoms of scalp psoriasis
- Development of an intercurrent condition or complication that could affect the safety of the patient or the validity of the evaluation of the patient's clinical state to an extent considered significant by the Investigator
- Signs and symptoms of possible HPA axis suppression
- Protocol deviations/violations that in the Investigator's opinion warrant discontinuation

Non-compliance with dosing need not be a reason for early termination. Patients who withdraw or are removed from the study will not be replaced. In the event a patient withdraws or is dropped from the study for any reason, the Investigator will request return of the unused product and report the reason for the discontinued participation.

When a patient discontinues early from the study, all study procedures required for the end of study should be performed at their last study visit. Patients who are discontinued from the study will be evaluated for safety and will be given, or referred for, appropriate treatment.

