9.6.15 Dosing Compliance

Dosing compliance will be checked by site staff at Visits 2 and 3. Patients taking fewer than 75% or more than 125% of the scheduled doses will be considered non-compliant with dosing. Compliance with dosing will be verified by the use of the patient diaries.

		Compliance Criteria	
Duration	Scheduled Doses	Not more than 125% (doses)	Not less than 75% (doses)
28 Days	28	35	21

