10.1.2 Safety Analysis of Potential HPA Axis Suppression

Dosing will be once daily for 28 days. Patients with normal adrenal function at baseline, use at least 21 doses of the study product and have data from a post-treatment cortisol response test will be included in the analysis. Patients who have not used 21 doses of the study product will be excluded from the primary analysis of HPA axis suppression.

The primary analysis of interest is to assess the proportion of patients considered to have demonstrated possible HPA axis suppression following treatment with the study medication. As a secondary analysis of the data a logistic regression of the proportion of patients in the study with HPA axis suppression will be performed with % scalp affected as a covariate. See Appendix D for results from the cortisol response test considered indicative of potential HPA axis suppression.

For all patients the actual amount of desoximetasone (mg) applied during the study will be calculated from recorded bottle weights and presented.

After the completion of 5 patients an interim analysis will be performed and presented.

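### The primary HPA set has a minimum dose count but no upper limit on time from last dose to test, so a test 6-10 days off drug can count as an end-of-treatment result

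*SAP*

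**What the plan says.** SAP 6.2.1 builds the primary HPA set from patients with normal baseline adrenal function who "use at least 21 doses of the study product and have data from a post-treatment cortisol response test will be included in the analysis". Protocol 10.1.2 sets the same conditions and adds the converse: "Patients who have not used 21 doses of the study product will be excluded from the primary analysis of HPA axis suppression".

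The plan for dosing is "Dosing will be once daily for 28 days". The figure of 21 is the lower edge of the compliance band in Protocol 9.6.15: "Patients taking fewer than 75% or more than 125% of the scheduled doses will be considered non-compliant with dosing".

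SAP 5 defines the primary outcome as the "absence or presence of adrenal suppression at the end of treatment". The test for it is at Visit 3, Day 29 ± 2. The only limit that either document puts on the interval from dose to test is a minimum of 12 hours (Protocol 9.5, 9.6.18 and Appendix D; SAP Appendix D). A separate rule in Appendix D of both documents requires at least 4 weeks between Cortrosyn tests.

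The SAP shells do record recency. T16.1.9.2 has a deviation category for product not applied about 24 hours before a visit, L16.2.5.1 lists the last-dose date, and L16.2.6.1 lists the test date and draw times. No exclusion, flag or sensitivity analysis is attached to any of these.

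On recovery, Protocol 7.3 states: "Recovery from steroid-induced adrenal insufficiency is usually rapid after the treatment is withdrawn". It gives no time course in days. Its only dated figure is from the adult spray study, in which all 3 suppressed patients were normal at the first follow-up, 28 days after treatment ended.

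**The concern.** A dose count limits how much drug was used, not when it was last used. Seven missed doses scattered over four weeks and seven missed doses at the end are treated alike, yet only the second pattern puts a drug-free week before the test. A patient with that pattern has exactly 21 doses, so is compliant under 9.6.15 and meets every condition for the primary set. A patient with fewer doses would not necessarily leave the study either (Protocol 9.3.4: "Non-compliance with dosing need not be a reason for early termination"), but would fall outside the primary set.

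If such a patient was suppressed on treatment and recovered before the test, T16.1.9.4 shows a No with full weight. With 5-10 evaluable patients, one such result can separate a report of some suppression from a report of none. In a maximal-use safety study that is the unfavourable direction for an error. Protocol 10.1 leaves the handling of missing, unused and spurious data to the SAP, and SAP 6.5 does not deal with this case.

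**Working it through.** **Dose cut-off (the plan's own figure).** 0.75 × 28 = 21 and 1.25 × 28 = 35. Both match the table in Protocol 9.6.15.

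**Days off drug.** Gap = test day − day of last dose, with daily dosing and Visit 3 on Days 27-31.

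| Dosing pattern | Last dose | Test day | Gap (days) |
|---|---|---|---|
| 21 consecutive doses from Day 1 | Day 21 | 27 / 29 / 31 | 6 / 8 / 10 |
| 21 consecutive doses from Day 2 | Day 22 | 27 / 29 / 31 | 5 / 7 / 9 |
| All 28 doses from Day 1 | Day 28 | 29 / 30 / 31 | 1 / 2 / 3 |

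If the 4-week spacing is kept after a Day 1 test, the earliest retest is Day 1 + 28 = Day 29. The first row then becomes 29 − 21 = 8 to 31 − 21 = 10 days. Scattered misses give shorter gaps. A late visit gives a longer one, since out-of-window tests are not excluded either.

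**Effect of one patient.** One suppressed patient scored No lowers the proportion by 1/N. Exact (Clopper-Pearson) 95% intervals:

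- N=5: 1/5 = 20% (0.5-71.6%) becomes 0/5 (0-52.2%), a drop of 20 points.
- N=10: 1/10 = 10% (0.3-44.5%) becomes 0/10 (0-30.8%), a drop of 10 points.

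**Illustration under assumptions.** Take a true on-treatment rate p = (1 + 2)/(12 + 9) = 3/21 = 14.3%, borrowed from the adult spray study in Protocol 7.3. Suppose k = 2 patients are tested off drug, and let r be the chance that a suppressed off-drug patient has recovered by the test. The documents do not give r, so a range is shown.

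- P(at least one case seen) = 1 − (1 − p)^(N−k) × (1 − p(1 − r))^k
- Expected observed rate = p(N − kr)/N

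For N=5 and r=1 the first is 1 − (18/21)^3 = 37.0% and the second is 14.3% × 3/5 = 8.6%.

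| r | N=5: P(≥1 case) | N=5: expected rate | N=10: P(≥1 case) | N=10: expected rate |
|---|---|---|---|---|
| 0 | 53.7% | 14.3% | 78.6% | 14.3% |
| 0.25 | 49.8% | 12.9% | 76.8% | 13.6% |
| 0.5 | 45.7% | 11.4% | 74.9% | 12.9% |
| 1 | 37.0% | 8.6% | 70.9% | 11.4% |

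**The case against.** The 21-dose threshold is a deliberate, pre-specified choice, the same in both documents. The 6-10 day gap needs every missed dose to fall at the end. The protocol asks for 28 days of daily use with a diary and for counselling of non-compliant patients at Visit 2, and no passage tells a patient to stop once the scalp clears. All of that stands: the scenario is an extreme, and 6-7 days arises only if the 4-week spacing is not kept.

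A reader might infer that nothing in the plan links the last dose to the test. The documents do not support that. T16.1.9.2 has the 24-hour deviation category, and with so few patients each gap can be found by subtracting two listed dates. A reader might also infer that any later test could feed the primary result. In fact T16.1.9.4 is titled for the end of treatment, L16.2.6.1 shows only Visits 1 and 3, and follow-up tests have their own listing, L16.2.6.2. What is missing is narrower: an interval derived for each patient, and a stated consequence for the analysis.

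The effect is also unproven. The chance of recovery by 6-10 days could be anywhere from 0 to 1, and the 10-20 points is simply 1/N for any misclassified patient. At N=10 with two off-drug patients and r=0.5, the expected shift from 14.3% to 12.9% is small beside an exact interval of 0-30.8% for 0/10. This argues for a supportive analysis rather than a changed primary set. It does not remove the gap in the rule, and a limit chosen after the results are seen would carry less weight.

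**Conclusion.** The inclusion rule can count a test taken 6-10 days off drug (8-10 days under the 4-week spacing) as an end-of-treatment result, against at most 3 days for a patient who took all 28 doses from Day 1. The analysis does nothing with that difference, and the SAP should address it before database lock.

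The gap figures assume 21 consecutive doses from Day 1 and an in-window visit. That the bias lowers the reported rate rests on the protocol's statement that recovery is usually rapid. Its size is unknown: one recovered patient costs 10 points at N=10 and 20 points at N=5, but the documents say neither how many patients would be tested off drug nor how many would have recovered. It would go too far to say that the planned analysis will hide suppression. The documents support only that it could, without the primary table showing it.

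**What to change.** 1. Leave the primary set as it is.
2. Derive the days from last dose to cortisol draw and add the column to L16.2.6.1. The dates are already collected.
3. Before database lock, pre-specify one supportive row in T16.1.9.4 limited to patients tested within 3 days of the last dose, the largest gap the visit window gives a patient who took all 28 doses from Day 1. A limit aligned with the SAP's 24-hour deviation marker is an alternative. Either way, say that the limit comes from the schedule and not from a recovery figure.
4. Footnote the row with the number of patients left out and their results, so that anyone found suppressed after a longer gap stays visible.
5. Reconcile the passages that conflict on test timing. Days 27-28 of the Visit 3 window fall inside the 4-week minimum after a Day 1 test, and the early-termination test at the last visit (Protocol 9.3.4) can do so too.

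Items 1-4 cost a few lines of SAP text, one derived variable and one table row. The downside is a smaller denominator in that row, and the limit is blunt. It would drop a patient with 27 doses ending on Day 27 and tested on Day 31 (gap 4 days), yet keep one with 21 scattered doses ending on Day 28. That is acceptable for a supportive row, not for a new primary set.

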6.2.2 Investigator Global Assessment

Patient will be examined to determine the severity of scalp psoriasis based on a global assessment of plaque elevation, scaling and erythema by the Investigator/designated clinician.

Investigator Global Assessment data will be summarized using frequency and percentage by visit.

Investigator Global Assessment data will also be listed by patient and visit.

6.3 Safety Analysis

Safety analysis will be conducted on all patients who applied at least one dose of study drug.

6.3.1 Adverse Events

All the adverse events (AEs) reported throughout the study will be coded and classified according to the MedDRA (Medical Dictionary for Regulatory Activities Version 1 or higher) coding dictionary. Each adverse event is to be evaluated for date of start and end, seriousness, severity, causal relationship with the study drugs, action taken and outcome.

**NOVUM PHARMACEUTICAL RESEARCH SERVICES
STATISTICAL ANALYSIS PLAN**

IND # 124879

Protocol/Study No. DSXS1538b/71615001

Desoximetasone 0.25% Shampoo

All AEs will be listed by patient.

A summary table of the number and percent of patients with AEs by system organ class, preferred term will be presented. Each patient will be counted only once within each preferred term.

A frequency summary table of the number of AEs by system organ class, preferred term, severity will be presented. Severity will be classified as “Mild”, “Moderate”, or “Severe”.

Similarly, a frequency summary table of the number of AEs by system organ class, preferred term, and relationship to a study drug will be presented. Relationship to a study drug will be classified as “Not Related” or “Related” where “Related” includes “Possible”, “Probable”, or “Definite”.

